A.3.2.2. Phlebotomy: During phlebotomy, in total less than 40mL will be collected at two different occasions. To assess LP eligibility (platelet count and INR), <10 mL blood will be drawn in 2 different tubes (~4mL in lavender top and ~3mL in light blue top) in participants' home. An additional 30 ml (three 10 mL heparin tubes) will be collected at the CRC, centrifuged to separate plasma from cellular material, divided into small samples, and frozen at -80C for future use. Blood will be stored in the SAGES freezer. Blood samples will be collected via peripheral venipuncture into sterile vacuum tubes using either a vacutainer or butterfly system. The first draw of blood will be collected in patients' homes by trained and experienced research staff or by a phlebotomy service affiliated with Hebrew SeniorLife. The second draw will be collected in the BIDMC CRC (at the same day as the LP or MRI) by nursing staff. Each procedure will last about 10 minutes. For the first blood draw hemolysis is not a concern and therefore the blood can be drawn in participant's homes. For the second blood draw immediate processing after the draw is essential and therefor the blood needs to be drawn at the CRC.

A.3.2.3. Lumbar Puncture (LP): During LP, 10-15 cc of CSF will be collected and centrifuged at low speed to remove any cellular contaminants, divided into aliquots and frozen in 0.5 ml polypropylene cryotubes for inflammatory and AD biomarkers. CSF will be stored at -80°C. The LP procedure, including consent, will take about 1-2 hours, and will be performed by one of the study Neurologists under supervision of [name] and with assistance from the CRC nurses as needed. During the LP, participants are placed in a left lateral position, with the back flexed, and knees are drawn up towards the chest, or sitting up and bent forward, whichever is easier for the participant. The lumbar region of the back will be cleaned with betadine, twice. Lidocaine 1% will be injected into the subcutaneous area between the L3-4 or L4-5 spinous process. Once the area is numb, a 24G or 25G atraumatic Sprotte LP needle will be placed and CSF will be collected. To clear any blood from minor

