Lab results: we also developed an incidental findings protocol to manage incidental findings on screening labs obtained for Lumbar Puncture (LP) eligibility. In general, the approach must be undertaken on a case-by-case basis. Incidental findings that could be life threatening, such platelet count less than 50K or INR greater than >5 (with symptoms), may be considered critical and necessitate referral to the Emergency Department or urgent call to PCP. Other IFs will be classified as (1) Urgent; (2) Routine; or (3) No Clinical Relevance based on the estimated risk of harm to the patient. Patients requiring urgent follow-up will not proceed with any study procedures. Study physician must make contact with PCP within 24 hours of abnormal test results, or sooner if patient is symptomatic (hemorrhage or thrombosis). Patients requiring Urgent Follow-up are temporarily excluded from the study; they may be reconsidered in six months time if clinical status has stabilized. Once the platelet or INR value is confirmed to be consistent and stable over time, he/she may proceed to RN adjudication (to confirm absence of bleeding, and thrombocytopenia-associated disorders, e.g. liver disease). If

confirmed by RN, patient may then proceed to LP. For patients requiring Routine Follow-up, a letter will be sent (as attached). Once the platelet or INR value is confirmed to be consistent and stable over time, he/she may proceed to RN adjudication (to confirm absence of bleeding, and thrombocytopenia-associated disorders, e.g. liver disease). If confirmed by RN, patient may then proceed to LP. All incidental findings are reported to the safety officer (TBD).

PET: Incidental findings on the amyloid PET (e.g., a structural abnormality) will be reviewed by a clinician who will follow our MRI incidental findings protocol, which has already been approved by the Institutional Review Board for our current scans (MRI), and our study physicians will inform the participant and their Primary Care doctor to arrange follow-up screening.

A.8. Information of other IRBs

The IRB of record for this multicenter study will be the BIDMC IRB. All other sites will have reliance agreements using the Online Reliance System SMART IRB: https://smartirb.org All PIs and field team members across sites meet at least weekly in person and have ad hoc phone call and meetings if needed for unforeseen emergencies or questions that need immediate attention. More information can be found in section B9.

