SAGES I SELECT Sub-group (N=148). General eligibility criteria for this subset of selected participants from SAGES I are described under A.3.2. Eligible participants from this subgroup will undergo specialized procedures including, lumbar puncture (LP), magnetic resonance imaging (MRI) scans and electroencephalogram (EEG) with non-invasive transcranial magnetic stimulation (TMS). Each of these procedures has specialized exclusion criteria and prior to each of these procedures subjects must complete a screening form designed to identify any contraindications and to assure safety. Before each procedure the respective teams and study doctors will review a safety protocol that includes the results of the screening procedures. MRI and TMS screening takes place during the inperson visit, in case of questions during a phone call of the MRI and TMS teams with the potential participant, and then again at the MRI and TMS visits. LP eligibility screening occurs during medical chart review, telephone screening, in-person visit, during potential adjudication through a study clinician for unclear eligibility, and during the LP visit through the study doctor. The SAGES I Select study screening forms details the timepoints of these exclusions. If a participant does not seem to remember her/his medical history well, we will ask for permission to reach out to a proxy using the Telephone Proxy Screener.

Additional exclusion criteria for Lumbar Puncture for the SAGES I SELECT subgroup: The SAGES I SELECT subgroup will undergo additional procedures, including a lumbar puncture. To verify eligibility, participants will undergo a medical history and medication review initially conducted by a research assistant, followed by adjudication by a clinician for unclear exclusion criteria. Finally, the study Neurologist will verify eligibility at the time of the LP visit.

The additional hard exclusion criteria for lumbar puncture include:

- Most recent platelet count within past 6 months < $50,000/\mu L$
- Most recent INR within past 6 months > 1.4
- Lumbar surgery with hardware
- Acute myocardial infarction or heart attack within 6 months
- New or unstable angina (chest pain) within 6 months
- Stroke or intracranial bleed within 6 months
- Ventriculo-peritoneal (VP) shunt for normal pressure hydrocephalus
- Currently taking anticoagulants and antiplatelet medication
- Severe shortness of breath at rest or lying down
- Continuous use of oxygen at home

- Totally blind

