- Mass in the brain

Soft exclusion criteria will be adjudicated by a clinician and include:

- Evidence of terminal illness (survival < 6 months)
- New onset of headaches within 6 months that awaken patient from sleep, or that are worse with coughing, sneezing, or bending over
- New onset of altered mental status within 6 months
- New onset of seizures within 6 months
- Evidence of focal neurological deficits (e.g. limb weakness hemiparesis, gaze palsy, visual field cut, pronator drift)
- Evidence of immunocompromised state (e.g. neutropenia/agranulocytosis, current chemotherapy, current immunosuppressive therapy or prednisone treatment, HIV/AIDS)
- Prior Lumbar Puncture within 12 months
- Hospitalization for possible acute myocardial infarction or heart attack within 6 months but no MD diagnosis confirmation
- Hospitalization for possible new or unstable angina (chest pain) within 6 months but no MD diagnosis confirmation
- Hospitalization for possible stroke of intracranial bleed within 6 months but no MD diagnosis confirmation
- Easy bruising or bleeding
- Active skin infections of lower back
- Taking anti-inflammatories (not including baby aspirin (81mg per day)
- Allergies to latex, tape, novocaine, lidocaine, or any other contact allergies
- Medication allergies
- BMI >>35
- History of back pain
- History of leg pain

Additional exclusion criteria for MRI and TMS-EEG include:

Hard exclusion criteria for MRI and TMS-EEG include:

- History of prior neurosurgery
- History of seizures or diagnosis of epilepsy, with the exception of a single seizure of benign etiology (e.g. febrile seizure) in the judgment of the investigator;
- Metal implants or devices such as a cardiac pacemaker or intracardiac lines, medication pump, any bio or neurostimulator, external fixation devices or bone growth stimulators
- Presence of any shrapnel or any metal fragment including bullet fragments anywhere in the body

Exclusion criteria for EEG only

None

Soft exclusion criteria will be adjudicated by MRI and TMS teams and include:

- Colonoscopy, endoscopy or interventional procedure within the past 30 days
- Ingestion of core temperature sensor or small pill camera within the past 30 days
- Metallic heart valves or any stents
- History of ear surgery or ear implant or prosthesis; cochlear implant
- History of eye surgery (cataracts, etc.) if before 1994 or eye implant or prosthesis (eye springs or wire, etc.)
- Metal injury to the eye
- Penile implant

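### A.7 lets a participant with a stable screening INR proceed to lumbar puncture after RN confirmation with no INR limit, while C.1.1 makes a most recent INR above 1.4 a hard exclusion

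*Protocol*

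**What the plan says.** Three parts of the protocol bear on the same blood result in SAGES I SELECT.

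- **A.3.2.2 (Phlebotomy)** gives the purpose of the home blood draw: "To assess LP eligibility (platelet count and INR), <10 mL blood will be drawn".
- **C.1.1 (hard exclusions for LP)** sets the limit: "Most recent INR within past 6 months > 1.4". The softer list is introduced separately: "Soft exclusion criteria will be adjudicated by a clinician and include". C.1.1 also sends unclear criteria to a clinician, and it ends the screening sequence with a physician: "Finally, the study Neurologist will verify eligibility at the time of the LP visit".
- **A.7 (Incidental Findings, lab results)** describes a procedure to "manage incidental findings on screening labs obtained for Lumbar Puncture (LP) eligibility". Findings that are not critical are classed as Urgent, Routine or of no clinical relevance. For the first class: "Patients requiring Urgent Follow-up are temporarily excluded from the study; they may be reconsidered in six months time if clinical status has stabilized". For the second, a letter is sent. Both routes then continue identically: "Once the platelet or INR value is confirmed to be consistent and stable over time, he/she may proceed to RN adjudication", and after that, "If confirmed by RN, patient may then proceed to LP".

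The only INR figure in A.7 is a value above 5 with symptoms, given as an example of a critical finding that may need emergency referral or an urgent call to the primary care physician.

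**The concern.** A.7 and C.1.1 both decide whether an LP goes ahead on the strength of one INR, and they use different tests. C.1.1 asks whether the value exceeds 1.4. A.7 asks whether it is stable and whether an RN finds no bleeding or related disorder. Stability does not mean that the value has normalised, so a persistently raised INR meets the A.7 test and fails the C.1.1 test.

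What is at stake is participant safety, not inference. In this subgroup the LP is done for research only, in people who were at least 70 at enrolment. Section B.5.1 lists bleeding into the CSF space among the rare risks of LP (less than 1%). Staff who follow A.7 would pass forward a participant whom C.1.1 tells the Neurologist to turn away.

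**Working it through.** No sample size, power or error rate is involved, so the check sets the two rules side by side and applies them to the same result.

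1. **Same measurement.** A.3.2.2 draws the INR to assess LP eligibility. A.7 covers abnormal findings on the labs drawn for that purpose. C.1.1 applies its limit to the most recent INR. All three concern the same result.

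2. **C.1.1 rule.** Exclude if the most recent INR is above 1.4.

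3. **A.7 rule, Urgent and Routine.** Release to LP if the value is stable and the RN confirms. The RN check covers absence of bleeding and of disorders associated with low platelets, with liver disease as the example. It does not compare the INR with a number.

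4. **Apply both to a stable, asymptomatic result with a clear RN check.** A repeat that confirms stability must lie close to the first value, and that repeat is then the most recent INR. The values below are illustrations.

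| First INR | Repeat, if stable | C.1.1 | A.7 |
|---|---|---|---|
| 1.4 or below | about the same | LP allowed | LP allowed |
| 1.8 | about 1.8, above 1.4 | LP barred | LP allowed |
| 2.5 | about 2.5, above 1.4 | LP barred | LP allowed |

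5. **The six-month wait does not reconcile them.** After the Urgent route's interval the first value may drop out of the C.1.1 window. But A.7 requires stability to be confirmed, and the confirming value is more recent and still above 1.4.

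6. **Adjudication does not reconcile them.** C.1.1 reserves adjudication for soft or unclear criteria. A measured INR above 1.4 is on the hard list and is not unclear.

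7. **Count.** A.7 has 2 written release routes. Routes with an INR limit: 0. Routes that refer to C.1.1: 0.

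8. **Platelets, for comparison.** A.7 names a count below 50K as potentially critical, and C.1.1 excludes below 50,000/µL. The two figures coincide, so the mismatch is specific to INR.

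**The case against.** The best defence is that A.7 manages incidental findings while section C sets eligibility, and that the protocol says so. A.3.2.1 sends all SAGES I SELECT participants through separate eligibility assessments for each procedure under section C. A permissive statement in A.7 can then be read as passing the participant to the next step, not as waiving a hard exclusion. Before each procedure the teams and study doctors review the screening results, and the Neurologist verifies eligibility at the visit. Current anticoagulant use is a separate hard exclusion, and the RN check names liver disease, so the group with a stable raised INR may be very small. This stands, and it limits the practical effect.

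A second argument is that A.7 may be meant only for values that are abnormal but inside the C.1.1 limits, so that no conflict arises. A.7 does not say this, and the reading is strained. The Urgent route stops all study procedures, requires contact with the primary care physician within 24 hours and excludes the participant temporarily. That hardly fits an INR of 1.4 or below. The point remains an inference, because the protocol does not give the Urgent and Routine cut-offs. They may sit in the separate incidental findings protocol that A.7 mentions.

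In the other direction, a reader might infer that the protocol approves LPs at any INR up to 5, or that participants will in practice have an LP above 1.4. The documents support neither. The figure of 5 is tied to symptoms and to emergency referral and is not an LP limit, and the later checks would have to overlook a listed hard exclusion.

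**Conclusion.** The inconsistency is real. In both release routes A.7 permits, on its wording, an LP that C.1.1 forbids, namely one in a participant whose INR is stable and above 1.4. It should be corrected because it concerns a safety threshold for a research-only procedure, and a later check that would probably catch the case does not make the two texts agree.

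Its size is modest. It applies to LP screening in SAGES I SELECT, with a target of 148. The number of participants with a stable INR above 1.4 cannot be derived from the protocol, and the safeguards in section C should make an LP above the limit a low-frequency event. No power calculation or analysis is affected.

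The conclusion assumes that A.7 as printed is what staff would follow. If the separate incidental findings protocol already limits release to an INR of 1.4 or below, the defect is confined to the wording of this document.

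**What to change.** In A.7, in both the Urgent and the Routine route, make the release sentence conditional. Suggested wording: *After RN confirmation the participant may go on to LP provided the hard exclusion limits in C.1.1 are met, including a most recent INR not above 1.4; otherwise amyloid PET is offered as in A.3.2.1.*

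Leave C.1.1 unchanged. The platelet limit need not be repeated in A.7, since the two sections already agree on it.

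The cost is a wording change at two places, with no new procedure, because PET for participants who are ineligible for LP is already planned in A.2 and A.3.2.1. Amyloid PET does not supply the CSF tau, NFL or inflammatory markers, but C.1.1 already accepts that loss for anyone above the INR limit.

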collected. At subsequent follow-up time points (POD2 and 1 month after surgery), two green tubes (20 cc) will be collected. Blood samples will be collected via peripheral venipuncture or central venous line (if available on PODs 1 and 2). When possible, blood will be obtained simultaneously with phlebotomy for routine clinical laboratory work, thereby eliminating the additional risk imposed by a separate phlebotomy for study purposes. Otherwise, an experienced staff member or phlebotomy services affiliated with Hebrew SeniorLife will collect the blood. Blood samples will be collected into sterile vacuum tubes using either a vacutainer or butterfly system, at the preference of the phlebotomist. All collected blood with be centrifuged to separate plasma from cellular products, divided into small samples, and frozen at -80C for future use.

A.4.6. MRI (n=180 SAGES II Subgroup): The SAGES II subgroup will undergo the MRI scan before hospitalization using the same procedure as outlined above for the SAGES I SELECT subgroup.

A.4.7. TMS-EEG: (n=180 SAGES II Subgroup): The SAGES II subgroup will undergo only one TMS-EEG session, as outlined above for the SAGES I SELECT subgroup, prior to surgery. A subgroup (n=102) will be invited for a second TMS-EEG 2 months after discharge from the index hospitalization and a third TMS-EEG 12-18 months after discharge.

Patients who are not able or decline to participate in the TMS-EEG session will be offered the option to participate in only collection of their resting-state EEG. They will be invited for a second and third EEG 2 months and 12 months after discharge from the index hospitalization. Verbal consent will be obtained from these patients.

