- Any aneurysm clips

- History of gastric bypass surgery after 2015
- Presence of any shunts (spinal, ventricular, peritoneal, subgaleal, etc.)
- Neurological implants
- Implantable defibrillator or implanted monitoring device
- Indwelling port, catheter, or feeding tube
- Tissue expanders or implants
- Implanted pump (insulin, pain medicine, chemotherapy, etc.)
- Dental work
- History of a fainting spell
- History of a head trauma that was diagnosed as a concussion or was associated with loss of consciousness
- Currently has hearing problems or ringing in the ears
- Problems with previous TMS procedures
- Patient is left-handed

Additional exclusion criteria for PET include:

• Prior scan with radioactive agents either for clinical or research purposes within 12 months, such that the total research-related radiation dose to the participant would exceed the limits set forth in the US Code of Federal Regulations (CFR) 21, Section 361.1.

C.1.2. SAGES II cohorts

SAGES II Cohort (N=460): The inclusion criteria for this newly enrolled surgical patients are outlined in section A.4 above. This group will undergo lumbar puncture during anesthesia if scheduled for spinal anesthesia, which has the same exclusion criteria as for lumbar puncture for the SAGES I SELECT subsample described in section C.1.1 above. If they receive PET because we could not obtain CSF, the same exclusion criteria for PET scans as outlined above in section C.1.1. will apply.

SAGES II Sub-group (N=180). This subgroup will undergo MRI and TMS-EEG with the same exclusion criteria and screening procedures as describe for the SAGES II specialized procedures described in section C.1.1. above

C.3. Gender and minority representation

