be found. In this case, we will follow our MRI safety protocol for incidental findings (approved by our IRB) developed by [name] for SAGES I and described below. Because an MRI machine uses powerful magnets, a person could be harmed if they entered the MRI scanner with metal in or on their body. To avoid any risks related to metal, patients will undergo a detailed safety screener and will be asked to change into scrubs prior to entering the scanner. Patients with certain implanted materials (e.g. cardiac pacemaker or pacemaker wires, implantable defibrillators, metallic particles in the body, vascular clips in the head or previous neurosurgery, prosthetic heart valves) will not be permitted to participate in the MRI substudy. Due to physical limitations of the MRI scanner, for safety reasons, participants whose abdomen, shoulder, or hip circumference is greater than 180 cm may not be able to undergo the MRI. This could make participants feel uncomfortable. If a participant indicates they have had an injury to the eye involving metal or an implant which may be contraindicated for MRI, an x-ray exam will be completed prior to the MRI. The risks of the x-ray involve minimal radiation exposure (approximately 0.84 milliSieverts total). A possible effect of this radiation could be a slight increase in the risk of cancer, from about 25% to 25.01% chance. Very high speed imaging methods can induce stimulation of peripheral nerves that may result in muscle twitches. This stimulation is due to electric fields induced by rapid magnetic field switching. FDA guidelines restrict the switching rate to a level that only rarely induces stimulation in subjects and our studies comply with these quidelines. While this sensation may be uncomfortable, it is not dangerous (see e.g. Schaefer DJ et al J. Magn Reson Imaging 12:20-29, 2000) and therefore does not affect the risk/benefit ratio. However, mentioned the occurrence of twitching in the consent form.

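### The MRI/TMS eligibility rules give two answers for defibrillators, aneurysm clips, heart valves and implanted pumps

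*Protocol*

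**What the plan says.** Section C.1.1 of the protocol sets hard and soft exclusions for MRI and TMS-EEG, each as one joint list for both procedures. Soft items go to the MRI and TMS teams for adjudication.

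- **Hard list.** It includes "History of prior neurosurgery" and "Metal implants or devices such as a cardiac pacemaker or intracardiac lines, medication pump, any bio or neurostimulator, external fixation devices or bone growth stimulators".
- **Soft list.** It includes "Metallic heart valves or any stents", aneurysm clips of any kind, neurological implants, shunts, "Implantable defibrillator or implanted monitoring device" and "Implanted pump (insulin, pain medicine, chemotherapy, etc".

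Section B.5.1, item 4 (risk of MRI), gives examples of implanted materials that keep a patient out of MRI. Pacemakers and implantable defibrillators are named, and the sentence ends "vascular clips in the head or previous neurosurgery, prosthetic heart valves) will not be permitted to participate in the MRI substudy".

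Section C.1.2 applies the same criteria to the SAGES II subgroup of 180. It describes them as belonging to the SAGES II procedures in C.1.1, but C.1.1 is the SAGES I section.

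On timing, SELECT participants have MRI and TMS about four years after their index surgery. In SAGES II the MRI and first TMS come before surgery (A.4.6, A.4.7). The later sessions come after it: "A subgroup (n=102) will be invited for a second TMS-EEG 2 months after discharge", with a third at 12-18 months.

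**The concern.** These lists decide who may enter a scanner or be stimulated, so each device needs one status. As written, a screener who refers a participant with a defibrillator for adjudication, and a team that then clears the MRI, have both followed C.1.1. The resulting scan is one that B.5.1 says will not take place. B.5.1 is also where the MRI risks and restrictions are described, so the risk description and the operative criteria do not match.

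The wording on metal implants raises a second, smaller question. Total hip and knee replacement are SAGES I index operations (A.3.1), and Project 1 describes SAGES II as a joint-replacement cohort (A.2.1). If the hard item reaches a hip or knee prosthesis, it affects SELECT participants and the SAGES II repeat TMS sessions. Neither list settles this.

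**Working it through.** No power or sample-size figure is involved. The check sets the status of each item in C.1.1 against its status in B.5.1.

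| Item | C.1.1 hard list | C.1.1 soft list | B.5.1 item 4 (MRI) | Result |
|---|---|---|---|---|
| Implantable defibrillator | not named | yes | barred | conflict between sections |
| Aneurysm clips / vascular clips in the head | not named | yes, any aneurysm clip | barred | conflict for aneurysm clips in the head |
| Metallic / prosthetic heart valve | not named | yes, if metallic | barred, if prosthetic | conflict for metallic prosthetic valves |
| Pump | yes, medication pump | yes, implanted pump | not named | conflict within C.1.1 |
| Stimulator / neurological implant | yes, any bio- or neurostimulator | yes, neurological implants | not named | possible overlap |

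**First three rows.** B.5.1 covers MRI only. The soft list is headed for MRI and TMS together, so it makes these devices adjudicable for MRI as well, and the conflict stands for MRI. Item 5 of B.5.1 (TMS risks) sets no device rule, so no such conflict arises for TMS alone. The terms for valves and clips are not identical in the two sections, but a metallic prosthetic valve or an aneurysm clip in the head falls under both.

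**Fourth row.** The hard item reads "Metal implants or devices such as a cardiac pacemaker or intracardiac lines, medication pump, any bio or neurostimulator". The soft item is "Implanted pump (insulin, pain medicine, chemotherapy, etc". An implanted pump delivering pain medicine fits both descriptions, so one participant is both excluded and adjudicable under the same section.

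**Fifth row.** An implanted neurostimulator is a neurological implant, but not every neurological implant is a stimulator. The overlap is likely but is not counted. Likewise, a head clip or ventricular shunt may imply the neurosurgery that the hard list bars, but neither soft item is confined to that case, so this is not counted either.

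**Count.** Three conflicts between sections plus one within C.1.1 gives 3 + 1 = 4. The lists apply to the SELECT subgroup (148) and the SAGES II subgroup (180): 148 + 180 = 328 planned participants at most. How many carry one of these devices is not stated.

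**Metal implants.** The hard item opens broadly, then gives examples: pacemaker, intracardiac lines, pump, stimulators, external fixation and bone growth stimulators. No joint prosthesis is named there or in the soft list. A.3.2.4 and B.5.1 allow an x-ray work-up for implants that might be contraindicated. Prostheses are therefore left without a stated status.

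**The case against.** The strongest defence is that soft means referred, not admitted. C.1.1 requires screening at the in-person visit and again at the procedure visits, with a safety-protocol review before each procedure. B.5.1 adds a detailed safety screener, and B.5.2 adds a metal detector. Anyone clearing a barred device would breach B.5.1, so the protocol does not simply permit it. This stands as far as it goes: the layers of screening lower the practical risk. They do not say which section prevails, and a review that applies the protocol's criteria inherits both answers.

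Three stronger inferences are tempting, and the documents do not support them.

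- **That the hard item bars the joint-replacement patients whom the study enrols.** Its examples are devices, lines and external hardware. A blanket metal bar would make much of the soft list pointless and would clash with the x-ray work-up. The SAGES II MRI and first TMS also precede the index operation.
- **That the SELECT or follow-up TMS samples would largely be lost.** SAGES I also enrolled spinal, vascular and bowel surgery (A.3.1), and SAGES II adds many abdominal, urologic and vascular operations (A.4). The protocol gives no surgical mix from which a loss could be computed.
- **That the recruiting hospitals would apply different rules.** The MRI and TMS-EEG sessions are held at one centre under the same supervision (A.3.2.1, A.4.1).

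**Conclusion.** The contradiction is confirmed for four items. Defibrillators, aneurysm clips in the head and metallic prosthetic valves are adjudicable in C.1.1 and barred from MRI in B.5.1. Pumps are both hard and soft within C.1.1. Stimulators and neurological implants are a possible fifth overlap. The conclusion rests on the wording alone, together with the joint heading of the soft list, which makes it apply to MRI. The number of participants affected is unknown.

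The prosthesis question is an ambiguity and not an established exclusion. It matters for SELECT, for the SAGES II TMS sessions after surgery, and for anyone who arrives with an earlier prosthesis. Which status is right for any device is a matter for the MRI and TMS safety staff, and no view on it is offered here.

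**What to change.** The responsible MRI and TMS safety staff should reconcile the hard and soft lists in C.1.1 with item 4 of B.5.1.

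1. Produce one list in which each device appears once with one status, stated separately for MRI and for TMS and using the same term throughout.
2. Have B.5.1 refer to that list instead of giving its own examples.
3. Reword the item on metal implants so that it names what it covers, and state explicitly how hip and knee prostheses are handled.
4. Correct the cross-reference in C.1.2 so that the SAGES II subgroup points to the reconciled list.

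The cost is protocol amendment wording and an updated screening form. No new procedure or staff is needed.
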